9.6. Data Management

The study will use existing databases with anonymized information on the individual patients. The processes for database management differ by the data source. Data extraction and analysis will be performed according to the standard practices of the data suppliers.

9.7. Data Analysis

Data analysis in the study will be descriptive. Continuous variables will be presented using appropriate descriptive statistics, such as mean, median, standard deviation and range. Categorical variables will be presented using percent and frequency tables. The rates and 95% CI of all study endpoints (i.e., risk minimisation indicators) will be calculated for the 2011-2015 period, using quarterly time blocks for the pre- and post- risk minimisation implementation periods. The rates will be calculated per 1000 domperidone-treated patients or as percentage of domperidone prescriptions, as appropriate. Paediatric data will be described separately from adult patients and rate of paediatric use will be calculated as fraction of overall domperidone utilisation. Missing values will be reported as missing and no imputation will be undertaken. All data analysis will be done in SAS using the version that is current when the analyses are done.

The rates for the primary endpoints of the study (the proportion of all prescriptions that are consistent with the revised label) will be calculated 4 ways to address uncertainty about 1) Unknown indication (is it assumed to be nausea and vomiting and therefore on-label, or is it assumed to be some other indication and therefore off-label) and 2) Duration of use that may be shorter than the days' supply (prescriptions with more than 7 days' supply assumed to

be intended for ≤ 7 days use, and provision of additional tablets for possible future episodes, and therefore on-label, versus assumed to be for >7 days use and therefore off –label):

- 1. Unknown indication assumed to be nausea and vomiting. Duration assumed to be ≤ 7 days (most optimistic scenario) meets the following conditions:
 - a. Prescription for nausea and vomiting or unknown indication but no recent diagnosis of GERD, gastroparesis, IBS, symptoms of postural hypotension in Parkinson patients, or as an aid to lactation;
 - b. Dose no higher than recommended;
 - c. No prescription to patients with certain cardiac and hepatic conditions; and
 - d. No co-prescription with CYP3A4 inhibitors or QT-prolonging drugs. (This considers such contraindicated co-medications only when they were prescribed ≤ the date of the domperidone prescription.)
- 2. Unknown indication assumed to be an off-label indication, duration assumed to be \leq 7days (an intermediate scenario) meets the following conditions:
 - Prescription for nausea and vomiting but no recent diagnosis of GERD, gastroparesis, IBS, symptoms of postural hypotension in Parkinson patients, or as an aid to lactation. Unknown indication will be assumed to be off-label (This differs from #1 above);
 - b. Dose no higher than recommended;
 - c. No prescription to patients with certain cardiac and hepatic conditions; and
 - d. No co-prescription with CYP3A4 inhibitors or QT-prolonging drugs (This considers such contraindicated co-medications only when they were prescribed ≤ the date of the domperidone prescription)
- 3. Unknown indication assumed to be nausea and vomiting, duration assumed to be the days' supply (an intermediate scenario) meets the following conditions:
 - Prescription for nausea and vomiting or for unknown indication but no recent diagnosis of GERD, gastroparesis, IBS, symptoms of postural hypotension in Parkinson patients, or as an aid to lactation (This is the same as in #1 above);
 - b. Duration (days' supply) ≤7 (This differs from #1 above and from #2 above, which don't examine days' supply)
 - c. Dose no higher than recommended;
 - d. No prescription to patients with certain cardiac and hepatic conditions; and

- e. No co-prescription with CYP3A4 inhibitors or QT-prolonging drugs. (Considers such contraindicated co-medications when prescribed ≤ the date of the domperidone prescription or prescribed within the days potentially covered by the domperidone prescription).
- 4. Unknown indication assumed to be an off-label indication, duration assumed to be the days' supply (most pessimistic scenario)
 - Prescription for nausea and vomiting but no recent diagnosis of GERD, gastroparesis, IBS, symptoms of postural hypotension in Parkinson patients or as an aid to lactation; Unknown indication assumed to be off-label (This differs from #1 above)
 - b. Duration (days' supply) ≤7 (This differs from #1 above and from #2 above, which don't examine days' supply.)
 - c. Dose no higher than recommended;
 - d. No prescription to patients with certain cardiac and hepatic conditions; and
 - e. No co-prescription with CYP3A4 inhibitors or QT-prolonging drugs. (Considers such contraindicated co-medications when prescribed ≤ the date of the domperidone prescription or prescribed within the days potentially covered by the domperidone prescription).

Rates of the study endpoints will be assessed for the pre-implementation period (1 April2013 through 31 March2014) and will be compared with the 1-year post-implementation period (1 October2014 through 31 March2015). In addition, each of the above label requirements that contribute to the primary endpoint will be compared for the same two 1-year periods.

In addition:

- The apparent indications, and the days supplied (≤7 days vs. >7 days) will be tabulated.
- 2. There will be a table showing the demographic characteristics, of the study population (sex, age group).

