9.3.2. Indication

Indication will be estimated from the diagnoses recorded in the time period preceding each domperidone prescription:

- The indication for the prescription will be defined as nausea/vomiting if the subject has a recorded diagnosis classified as nausea or as vomiting, on the day of the prescription or in the preceding 7 days.
- For those prescriptions whose indication is not defined as nausea/vomiting, the indication will be defined as off-label if the subject has, in the 2 months up to and

including the date of domperidone prescription, a diagnosis classified as one of the following:

- o GERD;
- Abdominal bloating, gastric dysmotility, delayed gastric emptying;
- o IBS;
- Suppressed lactation, failed lactation, lactation not established, decreased lactation, lactation problem; or
- Orthostatic hypotension and a diagnosis of Parkinson's disease.
- For those prescriptions not classified as above, the indication will be classified as unknown.

For a list of the diagnostic terms and codes that will be used to identify the above conditions, see Annex 6.

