9.3.6. A Composite Endpoint -All Label Requirements

Each prescription will be classified according to whether it appears to violate at least 1 of the above specifications, i.e., has a presumed indication that is off-label, has a dose that is above 30 mg/day (for ages \geq 12 years) or above 0.75 mg/kg/day (for ages <12 years), is written for a patient with a contraindicated condition, or appears to be prescribed concurrently with a medication contraindicated for concurrent use.

To accommodate the 2 areas of uncertainty described above (1] duration of domperidone use and 2] domperidone prescriptions for which the indication is unknown), the above classification will be done in the following 4 ways to reflect the possible combinations of:

- With consideration of days' supply being more than 7 days;
- Without consideration of days' supply being more than 7 days;
- With classifying subjects with an unknown indication as having an off-label indication; and
- Without classifying subjects with an unknown indication as having an off-label indication

This is described in more detail in Section 9.7.

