ANNEX 6: VARIABLES TO BE USED IN DATABASES

Condition	ICD-9 Codes	Text
Abdominal Bloating	536.3	Gastroparesis
GERD	530.11	Reflux esophagitis
GERD	787.1	Heartburn
GERD	787.2	Dysphagia
GERD	787.20	Dysphagia, unspecified
GERD	787.21	Dysphagia, oral phase
GERD	787.22	Dysphagia, oropharyngeal phase
GERD	787.23	Dysphagia, pharyngeal phase
GERD	787.24	Dysphagia, pharyngoesophageal phase
GERD	787.29	Other dysphagia
IBS	555	Regional enteritis
IBS	555.0	Regional enteritis of small intestine
IBS	555.1	Regional enteritis of large intestine
IBS	555.2	Regional enteritis of small intestine with large intestine
IBS	555.9	Regional enteritis of unspecified site
IBS	556	Ulcerative colitis
IBS	556.1	Ulcerative (chronic) ileocolitis
IBS	556.3	Ulcerative (chronic) proctosigmoiditis
IBS	556.5	Left-sided ulcerative (chronic) colitis
IBS	556.6	Universal ulcerative (chronic) colitis
IBS	556.8	Other ulcerative colitis
IBS	556.9	Ulcerative colitis, unspecified
Nausea and Vomiting	78.82	Epidemic vomiting syndrome
Nausea and Vomiting	536.2	Persistent vomiting
Nausea and Vomiting	564.3	Vomiting following gastrointestinal surgery
Nausea and Vomiting	643	Excessive vomiting in pregnancy

Condition	ICD-9 Codes	Text
Nausea and Vomiting	643.2	Late vomiting of pregnancy, unspecified as to episode of care or not applicable
Nausea and Vomiting	643.2	Late vomiting of pregnancy
Nausea and Vomiting	643.21	Late vomiting of pregnancy, delivered, with or without mention of antepartum condition
Nausea and Vomiting	643.23	Late vomiting of pregnancy, antepartum condition or complication
Nausea and Vomiting	643.8	Other vomiting complicating pregnancy
Nausea and Vomiting	643.8	Other vomiting complicating pregnancy, unspecified as to episode of care or not applicable
Nausea and Vomiting	643.81	Other vomiting complicating pregnancy, delivered, with or without mention of antepartum condition
Nausea and Vomiting	643.83	Other vomiting complicating pregnancy, antepartum condition or complication
Nausea and Vomiting	643.9	Unspecified vomiting of pregnancy
Nausea and Vomiting	643.9	Unspecified vomiting of pregnancy, unspecified as to episode of care or not applicable
Nausea and Vomiting	643.91	Unspecified vomiting of pregnancy, delivered, with or without mention of antepartum condition
Nausea and Vomiting	643.93	Unspecified vomiting of pregnancy, antepartum condition or complication
Nausea and Vomiting	787.03	Vomiting alone
Nausea and Vomiting	787.0	Nausea and vomiting

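### Sections 9.3.2 and 9.7 classify prescriptions carrying both a nausea/vomiting and an off-label diagnosis differently, and the Annex 6 codes do not match the conditions listed in 9.3.2

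*Protocol*

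**What the plan says.** Section 9.3.2 sets out a sequence. First: "The indication for the prescription will be defined as nausea/vomiting if the subject has a recorded diagnosis classified as nausea or as vomiting", on the prescription date or in the 7 days before. Second: "For those prescriptions whose indication is not defined as nausea/vomiting, the indication will be defined as off-label" if one of the listed conditions was recorded in the 2 months up to and including the prescription date. Anything left is unknown.

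Section 9.3.6 builds the composite on this result, since a prescription is in violation if it "has a presumed indication that is off-label". It then refers to 9.7 for detail.

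Section 9.7 defines four versions, meant to cover two uncertainties: unknown indication and duration of use. Versions 2 and 4 require "Prescription for nausea and vomiting but no recent diagnosis of GERD, gastroparesis, IBS" and so on. Version 1 requires "Prescription for nausea and vomiting or unknown indication but no recent diagnosis of GERD, gastroparesis, IBS" and so on, and version 3 is nearly identical.

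For codes, 9.3.2 says: "For a list of the diagnostic terms and codes that will be used to identify the above conditions, see Annex 6". One item on its off-label list is "Abdominal bloating, gastric dysmotility, delayed gastric emptying". The GERD block of Annex 6 contains rows such as "Dysphagia, oropharyngeal phase".

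**The concern.** Indication enters all four versions of the primary composite, and section 8.1 reports a risk ratio with confidence interval for each version in each country. If two sections give different answers for the same prescription, the primary proportion depends on which section is programmed. Different programmers working on the UK and IMS databases could also choose differently.

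The code list raises a second, separate question. It decides which diagnoses count as off-label. A listed condition without a matching code drops to unknown, which versions 1 and 3 count as compliant. A code that does not represent the listed condition does the reverse.

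**Working it through.** **Two rules side by side.** Cross nausea/vomiting in the last 7 days (NV) with a listed off-label diagnosis in the last 2 months (OFF), looking at the indication component only.

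| NV | OFF | 9.3.2: versions 1, 3 | 9.3.2: versions 2, 4 | 9.7: versions 1, 3 | 9.7: versions 2, 4 |
|---|---|---|---|---|---|
| yes | yes | compliant | compliant | depends on reading | **not compliant** |
| yes | no | compliant | compliant | compliant | compliant |
| no | yes | not compliant | not compliant | not compliant | not compliant |
| no | no | compliant | not compliant | compliant | not compliant |

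The rules disagree in the first row only. In versions 2 and 4 the exclusion clause cannot be a gloss on unknown indication, because unknown already fails there. It can only remove nausea/vomiting prescriptions. In versions 1 and 3 the clause may attach to unknown indication alone, which agrees with 9.3.2, or to both terms, which does not. The table assumes a 2-month window for 9.7, but 9.7 itself states none.

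**Effect on levels and on the risk ratio.** The plan has no figure to reproduce. Let *p* be the proportion meeting the indication component under 9.3.2 in versions 2 and 4, and *f* the share of those prescriptions that also carry an off-label diagnosis. Under 9.7 the proportion is *p*(1 − *f*). The ratio, post over pre as in section 9.5, is

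RR(9.7) = RR(9.3.2) × (1 − f_post) / (1 − f_pre).

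All values below are assumed: *p* = 30% pre and 33% post, so RR(9.3.2) = 0.33/0.30 = 1.10.

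| f pre | f post | 9.7 pre | 9.7 post | RR |
|---|---|---|---|---|
| 5% | 5% | 28.5% | 31.4% | 1.10 |
| 20% | 20% | 24.0% | 26.4% | 1.10 |
| 20% | 10% | 24.0% | 29.7% | 1.24 |
| 10% | 5% | 27.0% | 31.4% | 1.16 |
| 10% | 15% | 27.0% | 28.1% | 1.04 |

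With constant *f* the factor cancels and only the levels move. For drift alone to create a ratio of 1.10, the smallest effect in section 9.5's table, (1 − f_post)/(1 − f_pre) must equal 1.10. A fall from 20% to 12% does this: 0.88/0.80 = 1.10. From 10%, the share would have to fall to 1 − 1.10 × 0.90 = 1%. Below f_pre = 1 − 1/1.10 = 9.1% it cannot happen.

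**Annex 6 against 9.3.2.**

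- Bloating, dysmotility and delayed emptying: one row, labelled Abdominal Bloating, with code 536.3 and text Gastroparesis. Bloating and gastric dysmotility have no row of their own.
- GERD: nine rows, namely 530.11 reflux esophagitis, 787.1 heartburn, and seven dysphagia rows (787.2, 787.20 to 787.24, 787.29). None is worded as reflux disease itself.
- Visibly truncated codes: 78.82 is the only code with two digits before the point, while 094.82 keeps its leading zero. Codes 643.2, 643.8 and 643.9 each appear twice with different texts, while the parallel lactation rows keep their final zero (676.40, 676.50, 676.80, 676.90).

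If a share *u* of all prescriptions has only an unlisted reflux, bloating or dysmotility term and no nausea/vomiting, versions 1 and 3 rise by at most *u*. Purely for scale, if GERD were 30% of prescriptions and half were unlisted, *u* = 0.30 × 0.5 = 15 points. Both inputs are assumed. Dysphagia rows lower compliance instead.

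**Where the list applies.** Annex 5 gives ICD-9-CM for Spain, ICD-10 for France, Germany and Belgium, and Read codes for the UK. The ICD-9 list acts directly only in Spain.

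**The case against.** The strongest reply is that the conflict is one cell wide. It is certain only in versions 2 and 4, and it cancels from the risk ratio when the doubly diagnosed share is stable. The clause there could be a leftover from version 1, since version 2 flags only the handling of unknown indication as different. All of that is fair. The same remark can be turned round, though: if only unknown handling differs and the clause binds nausea/vomiting in version 2, it binds it in version 1 too. The text does not settle which rule was meant.

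On the codes, versions 2 and 4 already treat unknown as off-label, section 9.9.2 admits uncertain indication, and section 9.8 promises validation of coding. So a missing term is partly bracketed. The dysphagia rows are not bracketed, because they move prescriptions out of unknown in every version.

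Stronger readings are tempting, and the documents do not support them:

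- That reflux use is broadly counted as compliant and the results are inflated. Missing terms and dysphagia rows act in opposite directions, so the net direction is not fixed.
- That the risk ratio is biased. This needs a change in share between periods, and the protocol gives no evidence of one.
- That the 9.3.2 sequence is the correct rule. It would itself count nausea plus GERD as compliant in all four versions, and the exclusion could suit the most pessimistic version.
- That the IBS rows are wrong because they list regional enteritis and ulcerative colitis. The abbreviation list equates IBS with inflammatory bowel disease, so they fit.

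**Conclusion.** The point holds in limited form. Sections 9.3.2 and 9.7 give different answers for prescriptions with both diagnoses, unambiguously in versions 2 and 4, so the primary numerator is not uniquely defined. Compliance levels depend on the choice. The risk ratio depends on it only if the doubly diagnosed share changes between periods. The size cannot be determined from the protocol, and the percentages above are illustrations on assumed shares for one component of the composite.

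The Annex 6 mismatch is a separate and real defect in the operative list, of unknown net direction. Its direct reach is Spain. In the other four countries the effect depends on a mapping that is not shown. The truncated codes are minor, because the row texts identify what was meant.

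**What to change.** Choose one rule, sequence or exclusion, and state it in the same words in 9.3.2, 9.3.6 and all four versions of 9.7, so that the versions differ only on unknown indication and duration. Replace the undefined recent period in 9.7 with the 2 months of 9.3.2. Tabulate prescriptions with both diagnoses as a separate category by period and country, which shows whether their share drifts. Report the rule not chosen as a sensitivity analysis.

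Before extraction, align Annex 6 with the conditions in 9.3.2: give bloating, gastric dysmotility and reflux disease itself their own rows, or remove from 9.3.2 what will not be coded. Justify the dysphagia rows or test them in a sensitivity analysis. Correct 78.82 and the duplicated 643.2, 643.8 and 643.9 entries. Carry the corrected list into the ICD-10 and Read mappings.

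The cost is a wording change, a code-list revision, one extra table and one extra run per version. No additional data are needed.

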Data analysis in the study will be descriptive. Continuous variables will be presented using appropriate descriptive statistics, such as mean, median, standard deviation and range. Categorical variables will be presented using percent and frequency tables. The rates and 95% CI of all study endpoints (i.e., risk minimisation indicators) will be calculated for the 2011-2015 period, using quarterly time blocks for the pre- and post- risk minimisation implementation periods. The rates will be calculated per 1000 domperidone-treated patients or as percentage of domperidone prescriptions, as appropriate. Paediatric data will be described separately from adult patients and rate of paediatric use will be calculated as fraction of overall domperidone utilisation. All data analysis will be done in SAS using the version that is current when the analyses are done.

The rates for the primary endpoints of the study as the proportion of all prescriptions that are consistent with the revised label will be calculated:

- 1. Prescription for nausea and vomiting, or unknown indication but no recent diagnosis of GERD, gastroparesis, inflammatory bowel syndrome (IBS), symptoms of postural hypotension in Parkinson patients or as an aid to lactation;
- 2. Dose no higher than recommended;
- 3. No prescription to patients with certain cardiac and hepatic conditions; and
- 4. No co-prescription with CYP3A4 inhibitors or QT-prolonging drugs.

Note that additional analyses described in Section 9.3 will address the possibility that an unknown indication may be off-label, and the possibility that domperidone may be used for the entire number of days supplied.

Rates of the study endpoints will be assessed for the 1-year pre-implementation period (1 April 2013 through 31 March 2014) and will be compared with the 1-year post-implementation period (1 October 2014 through 30 September 2015). In addition, each of the above label requirements that contribute to the primary endpoint will be compared for the same two 1-year periods.

In addition:

- 1. The apparent indications, and the days supplied $(\leq 7 \text{ days vs.} > 7 \text{ days})$ will be tabulated.
- 2. There will be a table showing the demographic characteristics, of the study population (sex, age group).

Milestones

Milestones	Planned Date		
Start of data collection	Two months after protocol approval		
End of data collection	When data through SEP2015 become available for analysis (estimated as 4Q2016)		

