8.1. Primary Objectives

To describe the prescribing patterns before and after the changes to the domperidone label and distribution of a DHPC and estimate and compare the overall proportion of domperidone prescriptions before and after implementation of the risk minimisation measures regarding the following measures:

- Composite endpoint consisting of the following components:
 - Maximum daily dose;
 - Duration of use (>7 days);
 - Concomitant medications that prolong the QT-interval or are potent or strong CYP3A4 inhibitors;
 - Prescribing to patients with contraindicated conditions, e.g., moderate or severe liver disease, underlying cardiac diseases; and
 - Prescribing for off-label indications

Domperidone is used as needed, therefore the duration of use may not be the same as the number of days for which domperidone is supplied. As a result, duration of use will be assessed under the following 2 scenarios, which will be likely to bracket the actual (but unknown) situation:

- 1. Domperidone is used only for as little as 1 dose after it is prescribed, and
- 2. Domperidone is used for the entire number of days supplied.

This is intended to bracket the plausible values for duration of use

Primary test statistic: In each country studied, the change in the proportion of all prescriptions that comply with the label based on the above composite endpoint during the 12 months before the label change versus the 12 months after the label change is the primary statistic to be evaluated as a measure of the effectiveness of the label change in that country. The statistic will be evaluated as a risk ratio, i.e., as the ratio of the proportion of prescriptions that met all conditions in the composite endpoint between 1 April 2013 and 31 March 2014 and the proportion of prescriptions that met all conditions of prescriptions that met all conditions in the composite endpoint between 1 October 2014 and 30 September 2015. The point estimate and 95% confidence interval for the above risk ratio will be reported. There are several versions of the composite endpoint are implemented in the databases and the risk ratio (point estimate and 95% confidence interval) will be reported for each. Note that the term "risk ratio" is being used in the sense of a ratio of probabilities (the probability of a prescription being consistent with the new label).

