9.2.2. Study Period

The study period will be divided into a background period and pre- and post- implementation periods of risk minimisation measures as follows:

- A background period (1 January 2011 through 31 March 2013)
- A 1-year pre-implementation period of risk minimisation measures (1 April 2013 through 31 March 2014)
- A 1-year post-implementation period of risk minimisation measures (1 October 2014 through 30 September 2015)

The period during which the label change took place and the DHPC was sent will be used as the period during which the risk minimisation measures were implemented (1 April 2014 through 30 September 2014).

Because the amendments to the product information were suggested by the PhVWP in October 2011, the study will track prescribing pattern changes from 1 January 2011 (a time that preceded most of the discussion and implementation of the label changes, i.e., a background period) through 30 September 2015.

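### Section 9.7 ends the one-year post-implementation window after six months (31 March 2015), contradicting its own label and the 30 September 2015 end date in Sections 8.1 and 9.2.2 and the Abstract

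*Protocol*

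**What the plan says.** Section 9.7 (Data Analysis) sets the dates for the pre/post comparison of all study endpoints. On the pre side it takes 1 April 2013 to 31 March 2014, as the other sections do. For the post side, it says that the rates "will be compared with the 1-year post-implementation period (1 October2014 through 31 March2015"). The next sentence adds that the individual label requirements "will be compared for the same two 1-year periods".

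Three other places give a different end date:

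- Section 9.2.2 (Study Period): "A 1-year post-implementation period of risk minimisation measures (1 October 2014 through 30 September 2015").
- Section 8.1 (Primary Objectives), which defines the primary statistic, counts prescriptions that met all conditions "in the composite endpoint between 1 October 2014 and 30 September 2015" and describes the contrast as "during the 12 months before the label change versus the 12 months after the label change".
- Section 4 (Abstract, Data Analysis): "1-year post-implementation period (1 October 2014 through 30 September 2015").

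The milestones (Section 6) plan for data through September 2015. Section 8.2, which lists the component analyses, gives no dates. The windows for comparing the components are stated only in Section 9.7 and the Abstract, and these two disagree.

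**The concern.** The wrong date stands in the section that specifies the analysis, and it governs the comparison of the composite and of each component. The protocol then contains two post-implementation windows, and an analysis using either could be described as following it. The study takes five countries from different databases, so the windows could also be cut differently between countries.

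The primary measure is a ratio of two proportions, and no covariate adjustment is described. The ENCePP checklist (Annex 2) marks both seasonality and adjustment for confounding as not applicable. Balanced 12-month windows are then what keeps season out of the ratio. On the Section 9.7 dates, the pre period covers all four quarters and the post period only October to March. Any seasonal difference in why, how or to whom domperidone is prescribed would enter the ratio as if it were an effect of the label change.

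The shorter window also departs from Section 9.5, where Table 2 assumes equal numbers of prescriptions before and after.

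**Working it through.** **Length of the windows** (inclusive day counts from the stated dates)

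| Window | Source | Dates | Days |
|---|---|---|---|
| Pre | 8.1, 9.2.2, 9.7, Abstract | 1 Apr 2013 to 31 Mar 2014 | 365 |
| Post | 9.7 | 1 Oct 2014 to 31 Mar 2015 | 182 |
| Post | 8.1, 9.2.2, Abstract | 1 Oct 2014 to 30 Sep 2015 | 365 |

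The one-year length stated in Section 9.7 is not reproduced by its own dates. It is reproduced by the end date used in the other three places. The difference is 365 − 182 = 183 days (April to September 2015), or 183/365 = 50% of the post period.

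**Power in the smallest database**

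Inputs from Section 9.5: 22,000 prescriptions (Belgium, 2015 data), two-sided 5% test, baseline compliance 10%, risk ratio 1.1 (so 10% versus 11%), and a claim of at least 90% power. Assumptions: 22,000 a year applies to both periods, accrual is even over the year, and prescriptions are independent.

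Formula (normal approximation, pooled variance under the null hypothesis):

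power = Φ{ [ (p2 − p1) − 1.96·SE0 ] / SE1 }, where

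- SE0 = √[ p̄(1 − p̄)(1/n1 + 1/n2) ], with p̄ the pooled proportion;
- SE1 = √[ p1(1 − p1)/n1 + p2(1 − p2)/n2 ].

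1. Full-year post window, n1 = n2 = 22,000. p̄ = 0.105, SE0 = 0.002923, SE1 = 0.002922. The argument is (0.01 − 0.005729)/0.002922 = 1.46, so power = 92.8%. This agrees with the protocol's claim of at least 90%.
2. Section 9.7 window, n1 = 22,000 and n2 = 22,000 × 182/365 ≈ 10,970. p̄ = 0.1033, SE0 = 0.003558, SE1 = 0.003608. The argument is (0.01 − 0.006973)/0.003608 = 0.84, so power = 79.9%.
3. Section 9.7 window, 20% versus 22%: SE0 = 0.004733, SE1 = 0.004787. The argument is (0.02 − 0.009276)/0.004787 = 2.24, so power = 98.7%.
4. Section 9.7 window, 30% versus 33%: power above 99.9%.

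**Season**

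The documents give no compliance figures by quarter or season. Neither the direction nor the size of a seasonal bias can be calculated from them.

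**The case against.** The best reply is that this is a slip, not a design choice. Section 8.1 defines the primary statistic, gives the full 12 months with explicit dates, and says 12 months on each side. Section 9.2.2 and the Abstract agree, and data collection is planned through September 2015. Even in Section 9.7 the wording around the date describes a year. The amendment log records a clarification of the period dates for the Abstract and Section 9.2.2 only, which fits a missed edit in Section 9.7. Section 9.8 also provides for a reviewed statistical analysis plan and independent review of programming, so the conflict might well be noticed.

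Most of this stands. It makes the intended date clear and the harm conditional. It does not remove the contradiction from the analysis section.

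A reader might infer three stronger things, none of which the documents support:

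- *That the primary comparison will be a half-year against a year.* This follows only if the Section 9.7 date is preferred to the definition in Section 8.1.
- *That the evidence from April to September 2015 is lost.* Section 9.7 also calls for quarterly rates with confidence intervals over 2011–2015, and Section 9.2.2 tracks prescribing through 30 September 2015. Those months would drop out of the pre/post comparison only. The quarterly series might reveal a seasonal pattern, but it would not correct the ratio.
- *That a seasonal bias of a given size is to be expected.* Any such figure would rest on invented compliance rates.

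**Conclusion.** The point holds as an internal contradiction. Section 9.7 gives a 182-day window, calls it a year, and conflicts with three other statements of the end date in the same protocol. This needs no assumptions.

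The consequences depend on the Section 9.7 date being followed. In that case the comparisons would be unbalanced over the seasons and would leave out about half of the post period. The loss of power from about 93% to about 80% is specific to the smallest database, 10% baseline compliance and a ratio of 1.1, under the assumptions of 22,000 independent prescriptions a year and even accrual. At baseline compliance of 20% or more the loss is of no practical importance for that ratio. Season is the more general concern, because it does not shrink with sample size, but its size is unknown.

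The correction should be made because the date fixes the comparison window for every endpoint, not because a large bias has been shown.

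**What to change.** In Section 9.7, change the end of the post-implementation window from 31 March 2015 to 30 September 2015. The section then matches Sections 8.1 and 9.2.2 and the Abstract, both windows are 12 months long, and each covers all four quarters. Make the change before data extraction, and carry the same dates into any statistical analysis plan and into the programming specification for each database.

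The cost is one date in the protocol. It needs no further data, since collection is already planned through September 2015, and no additional analysis.
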